Subjects will be enrolled per the inclusion/exclusion criteria. Subjects will be screened and consented prior to their stent placement procedure for stone disease. Patients will be formally enrolled and randomized post-operatively based on no severe complications intra-operatively, such as extensive extravasation, hematoma could confound the pain and compromise the results. All subjects will complete at baseline and all follow-up visits: 1) the Incontinence Symptoms Severity Index (ISSI), 2) American Urologic Association symptom score (AUASS) 3) the Visual Analog Scale (VAS) to represent change in acute pain 4) the Patient Global Impression of Severity (PGI-S) quality of life scale 5) a voiding diary for 1 to 3 days preceding day, 7, and stent removal visits, and then 14 days after the stent removal (if done by day 28) to obtain base line diary and 6) a narcotic log starting after surgery through 14 days after stent removal (if done by day 28). The ISSI will be used to assess any change in voiding symptoms. This scale has been validated to efficiently capture and quantify urological symptoms⁷. The voiding diary is used to capture the number of micturition per day, urgency and associated incontinence. The VAS has been validated to measure changes in acute pain that are clinically significant⁸. The PGI-S has been proven to efficiently summarize a patient's perception to change in severity in regards to lower urinary tract symptoms (LUTS)⁹. Subjects will undergo a blood draw prior to stent placement (complete blood count (CBC), comprehensive metabolic panel (CMP) and urine analysis (sugar, protein, WBC/RBC, bacteria)) to verify eligibility. These laboratories will not be repeated if they were performed routinely as a part of preoperative work up. 100 subjects will be equally randomized into 1 of 2 study groups, active treatment with Myrbetriq™ or administration of a placebo. A daily 50 mg dose of Myrbetriq™ will be administered in the treatment group for up to 4 weeks initiated on the day of stent placement. A 50mg dose was chosen as the initial dose due to the acute nature of the symptoms which do not require long term therapy. It has been shown that Myrbetriq™ 50 mg taken orally once daily has superior efficacy in treatment of LUTS when compared to placebo by week 4 (the duration of this study) and this effect was maintained. A 50mg dose was proven to be safe and effective to patients in Phase III trials^{10,11}. Both study groups will receive similar prescriptions of narcotics in dose and number. Patients will be given a log to record use of narcotics. If a different form of narcotics is prescribed due to side effects or allergic reaction, a narcotic analgesia converter calculator will be used to adjust for the doses, for analysis purposes. Post-operative symptoms and pain medicine intake will be assessed at days 1, 7 via telephone interview, and with a clinic visit the day of stent removal (or day 14 if stent removal postponed) and via phone 14 days after the stent is removed. If patient is to have stent removed on day 28, or later, the patient will receive a day 21 telephone call to obtain post-operative pain and pain medicine intake, as well as questionnaires. They will remain on study drug until day 28. Use of prescription, over-the-counter and supplemental medications for pain control will be captured using self-report and direct observation/recording of medication labels by the study team. These interviews will be conducted by study staff who will be blinded to the subject's treatment. Subjects will complete

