
the ISSI, the AUASS, voiding diary, VAS, narcotic log, and PGI-S during these follow ups. The day 14 assessments will be collected prior to their stent removal procedure.

Study Subjects

Patients will be identified and recruited through the SIU urology clinics and St. John's Hospital during a 24 month enrollment period. Participation in this study will be completely voluntary. Male and female subjects presenting with planned stent placement for ureteral obstruction or post-ureteroscopy procedures for stone, except for those undergoing uteropelvic junction obstruction, will be evaluated for participation. Should the patient decline to participate, their choice will not change their prescribed course of standard urologic treatment. After review and approval by the local Institutional Review Board, the study will enroll 100 patients that meet the inclusion criteria below and agree to participate. Annually, the study investigators perform approximately 350 stenting procedures (based on 2 previous years of clinical data).

Inclusion Criteria

1. Age \geq 18.
2. Subject scheduled to undergo a ureteral stent placement for ureteral obstruction or post-ureteroscopy procedure.
3. Otherwise healthy subjects who are able and willing to participate in the study.
4. None of the planned interventions are documented in the labeled contraindications, warnings and precautions of the study drug.

Exclusion Criteria

1. Does NOT give consent.
2. Subject is using prohibited medications which cannot be stopped safely at the screening visit. Subject is excluded if using restricted medications not meeting protocol-specified criteria:
 - (i) Phytotherapy for BPH or a 5-alpha reductase inhibitor within 3 months, with persistent urinary symptoms and AUASS more than 7.
 - (ii) Taken an oral alpha agonist, anticholinergic or cholinergic medication within 5 days of the first screening visit with the following exception(s): a singular dose given in ER or on the hospital floor prior to procedure, topical anticholinergic eye drops used for glaucoma or inhaled anti-cholinergic used for COPD.
 - (iii) Taken tricyclic antidepressants within 2 weeks of the first screening visit.
 - (iv) Taken an estrogen, androgen, or any drug producing androgen suppression, or anabolic steroids within 3 months with the following exceptions: any topical creams for local treatment.
3. Post void residual volume $>$ 350 mL.

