4. Female subject is breastfeeding, pregnant, intends to become pregnant during the study, or of childbearing potential is sexually active and not practicing a highly reliable method of birth control.
5. Subject has known neurogenic bladder.
6. Subject with uncontrolled chronic pain problems or on chronic pain medications.
7. Subject has significant stress incontinence or mixed stress/urgency incontinence where stress is the predominant factor as determined by the investigator (for female subjects confirmed by a cough provocation test).
8. Subject has an indwelling catheter or practices intermittent self-catheterization.

9. Known primary neurologic conditions such as multiple sclerosis, Parkinson's disease, diabetic neuropathy or any neurological diseases known to affect bladder function.
10. Subject has evidence of a symptomatic active urinary tract infection, chronic inflammation such as interstitial cystitis, previous pelvic radiation therapy or previous or current malignant disease of the pelvic organs, or bladder stones (which can be located in different anatomical location and can cause LUTS similar to bladder infection and pain related to their location in the bladder which could mask the treatment effect).
11. Subject who is currently under active treatment with botulinum toxin (and all other bladder paralytics) intravesically.
12. Subject has moderate to severe hepatic impairment [ALT (SGPT) or AST (SGOT) value greater than 3 times the upper limit of normal in the clinical center lab; confirmed on a second measurement].
13. Subject has severe renal impairment or End Stage Renal disease (i.e., creatinine greater than 2.0 mg/dl).
14. Subject has severe uncontrolled hypertension (defined as systolic blood pressure ≥ 180 mmHg and /or diastolic pressure ≥ 110 mmHg).
15. Subject has a clinically significant abnormal ECG in their chart or has a known history of QT prolongation or currently taking medication known to prolong the QT interval. Any patient taking Digoxin.
16. Subject has a known or suspected hypersensitivity to Mirabegron or any of the inactive ingredients.
17. Subject has a concurrent genitourinary malignancy, or active cancer (except noninvasive skin cancer) within the last 5 years prior to screening. Men with a history of prostate cancer regardless of curability are not eligible.
18. Subject has been treated with an experimental device within 30 days or received an experimental agent within the longer of 30 days or five half-lives.

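### The criteria lists that govern enrolment omit the ureteropelvic junction exception and the stone wording given in the narrative, and are silent on a ureteral stent already in place at baseline

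*Combined protocol and SAP*

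**What the plan says.** **Who is enrolled, by the lists.** Inclusion Criteria, item 2: "Subject scheduled to undergo a ureteral stent placement for ureteral obstruction or post-ureteroscopy procedure". It carries no stone qualifier, no UPJ exception and no condition on an existing stent.

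**Who is enrolled, by the narrative.** Study Methods: "Subjects will be screened and consented prior to their stent placement procedure for stone disease". Study Subjects describes "planned stent placement for ureteral obstruction or post-ureteroscopy procedures for stone" and then adds "except for those undergoing uteropelvic junction obstruction, will be evaluated for participation" (the source spelling; I read it as ureteropelvic).

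**Which text governs.** Study Methods: "Subjects will be enrolled per the inclusion/exclusion criteria". Study Subjects: "the study will enroll 100 patients that meet the inclusion criteria below and agree to participate". Randomization Schema likewise has the coordinator obtain the subject ID only once all inclusion and exclusion criteria are met.

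**Existing stent.** The nearest criterion is Exclusion Criteria, item 8: "Subject has an indwelling catheter or practices intermittent self-catheterization". It does not name a ureteral stent.

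**Baseline.** The assessment schedule places ISSI, VAS, PGI-S and AUASS in the baseline/stent placement column. The voiding diary has no entry there; Study Methods takes its baseline 14 days after stent removal, if removal is done by day 28. Change from baseline in ISSI at 1 and 2 weeks is a primary endpoint, and Statistical Analyses compares it between arms with an independent t test.

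**The concern.** Eligibility is checked against the numbered lists, but the one express exception to the target population sits only in a recruitment paragraph. Someone verifying eligibility from the lists could pass a patient whom that paragraph sets aside. The pilot is meant to supply an effect size and feasibility information for a larger study in the same population, so that population should be defined in one way.

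The stent question is separate. The trial's premise is that a stent causes storage symptoms and pain. A patient who arrives with one already in place (for an exchange, or for ureteroscopy after earlier stenting) may score those symptoms at baseline, while a patient without one does not. The two change scores then measure different things: continued stenting in one case, new stenting in the other. Nothing in Statistical Analyses records or adjusts for this.

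**Working it through.** **Step 1. Compare the texts.**

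| Question | Study Methods | Study Subjects text | Inclusion 1-4 and exclusions 1-21 |
|---|---|---|---|
| UPJ obstruction | not mentioned | set aside | not mentioned |
| Non-stone ureteral obstruction | excluded by implication | unclear | admitted |
| Ureteral stent already in place | not mentioned | not mentioned | not mentioned |

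- UPJ: the Study Subjects sentence names UPJ as an exception to the indications it has just listed. This implies that the authors thought UPJ would otherwise be covered, and item 2 repeats those indications without the exception.
- Non-stone obstruction: exclusions 10 and 17 remove pelvic radiation, pelvic-organ malignancy, genitourinary malignancy and active cancer. Benign obstruction, such as a stricture, is left in. In Study Subjects, the words about stone may qualify both indications or ureteroscopy alone.
- Existing stent: this is silence. No text includes or excludes such patients.

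**Step 2. The plan's own power figure.** Inputs from Statistical Analyses: SD 4.17 per group, 50 per group, two-sided alpha 0.05, 80% power, a 25% ISSI difference. The mean to which 25% applies is not given, so the 80% cannot be verified directly. Solving for the difference:

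4.17 × √(2/50) × (1.960 + 0.842) = 2.34 points (2.36 by the t distribution)

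The implied reference mean is 2.34 / 0.25, about 9.35 (9.44 by t). I hold 2.34 fixed below.

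**Step 3. Illustration of mixed baselines.** Assumptions, none of them in the documents: a share f is already stented at baseline; their change score is shifted by k SDs, equally in both arms; 4.17 is the SD of change within each subgroup. Then

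SD of change = 4.17 × √(1 + f(1−f)k²)

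For f = 20%, k = 1: 4.17 × √1.16 = 4.49. Power by the normal formula is Φ(2.34 / (4.49 × 0.2) − 1.96), about 74%.

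| f | k = 0.5 | k = 1 | k = 2 |
|---|---|---|---|
| 10% | SD 4.22, power 79% | SD 4.35, power 77% | SD 4.86, power 67% |
| 20% | SD 4.25, power 78% | SD 4.49, power 74% | SD 5.34, power 59% |
| 30% | SD 4.28, power 78% | SD 4.59, power 72% | SD 5.66, power 54% |

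The k = 2 column is extreme: 2 × 4.17 = 8.34 points, almost the whole implied reference mean of 9.35.

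**Step 4. Bias or variance.** Stent status at baseline is fixed before assignment, so randomization balances it in expectation. The f(1−f)k² term is the extra variance from chance imbalance and within-arm spread. Under the same additive assumption, putting the stent indicator in the model removes that term.

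**Step 5. Which endpoints.** The mixing applies to ISSI, VAS, PGI-S and AUASS, which are scored at placement. Micturition and incontinence episodes use a diary baseline taken after stent removal, so a stent present at enrolment does not enter it in the same way.

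**The case against.** The UPJ exception stands directly above the criteria and decides who is evaluated at all, so such patients may be filtered out before the lists are opened. This is fair. It means that the enrolled group may depart from the intended one; a reader might infer that it does, and the documents do not show that.

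A reader might also infer that the narrative excludes all non-stone obstruction. It does not clearly do so. One phrase in Study Methods points that way. The Study Subjects sentence can be read as admitting any ureteral obstruction, and a UPJ exception would be largely redundant if only stone patients were meant. The planned larger study is described as being in this population, not as a stone trial. What stands is the ambiguity.

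Patients stented before ureteroscopy for stone lie inside the stone population, and an exploratory pilot may reasonably take them. That also stands: the lists contradict nothing here, and excluding these patients, or requiring a stent-free interval, would be a design preference. The 14 days in the protocol is a follow-up and diary time, not a stated recovery period.

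Finally, the power figures rest on an assumed share and shift. The plan does not call 4.17 an SD of change. If it came from a mixed group, some of this spread would already be in it.

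None of this puts the UPJ exception into the lists, or says how a stented baseline is to be treated.

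**Conclusion.** The point holds in a limited form. The lists that govern enrolment omit an exception stated in the narrative (UPJ) and do not settle whether other obstruction must be stone-related. A patient with UPJ obstruction or benign non-stone obstruction can meet every listed criterion. This rests on the text alone and needs no assumption.

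The lists are also silent on an existing ureteral stent, so the questionnaire baselines may mix two states. It is tempting to conclude that the treatment comparison is biased, or that a definite amount of power is lost; neither follows. Randomization keeps the contrast unbiased in expectation. The cost is added variability in the ISSI change score and a less clearly defined population. The size cannot be derived, because the documents give neither the share already stented nor the shift in their scores. For shifts of 0.5 to 1 SD and shares of 10-30%, the illustration runs from 79% down to 72%, against a nominal 80%.

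**What to change.** 1. Add the UPJ exception to Exclusion Criteria, in line with Study Subjects.
2. Reconcile Inclusion Criteria item 2 with Study Methods and Study Subjects on whether obstruction must be stone-related, and use the same wording in all three places. The documents do not say which reading is intended, so the investigators must decide.
3. Record at baseline whether a ureteral stent is already in place. The medical and surgical history reviewed at that visit should supply this.
4. Replace the unadjusted t test of ISSI change with an analysis of covariance on treatment, baseline ISSI and the stent indicator.

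No exclusion of already-stented patients and no stent-free interval is required.

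**Cost.** One extra baseline field and two covariates: the residual degrees of freedom go from 98 to 96 with 100 patients. The eligible pool may be slightly smaller. The plan seeks 100 patients from about 350 procedures a year over 24 months: 100 / (2 × 350) = 14.3%. That is before exclusions and refusals, and the documents do not give the share with UPJ or non-stone obstruction.

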19. Unable to follow protocol directions due to organic brain or psychiatric disease.
20. Intra-operative complications that require hospital admissions.
21. History of alcoholism or any other substance abuse, which, in the opinion of the investigator, would affect compliance with the protocol.

Assessment or Procedure	Baseline/ Stent Placement	Post-Op Day 1 (phone)	Post-Op Day 7 (phone)	Stent removal (Post-Op Day 14 if stent not removed) visit	Post- Op Day 21 (phone) (if stent not removed)	2 weeks after stent removal or Day 42 (phone)	Early Withdrawal
Informed Consent	X						
Verify Eligibility	X						
Review Medical & Surgical History	X						
Physical Examination (H & P)	X			BP and HR only			BP and HR only
Review Prior & Current Medications	X	X	X	X	X	X	X
Review Adverse Events		X	X	X	X	X	X
ISSI	X	X	X	X	X	X	X
VAS	X	X	X	X	X	X	X
PGI-S Quality of Life Scale	X	X	X	X	X	X	X
AUASS	X	X	X	X	X	X	X
Voiding diary			X	X		X	
Pain log		X	X	X	X	X	X
Laboratory screening tests (hematology & chemistry)	X						
Randomization	X						
Study drug administration/Accountability	X			X		X only if you have drug	X

Visit window for all visits are +/- 2 days

Study Procedures

Informed Consent

All participants will be required to provide written informed consent. The study staff will introduce the study after being informed the subject is potentially eligible. The study coordinator and/or study staff will review the informed consent document with the subject. The subject will be provided information related to the study purpose, procedures, potential risks and benefits to participation, voluntary nature of their potential participation and provide them an opportunity to ask and have answers to all questions prior to obtaining any signature. A study investigator will be available to answer any questions. Subjects will not be compensated for participation and there are no additional costs to subjects for participation in the study.

Randomization Schema

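### Exclusion 13 applies one creatinine cap to all adults, so item 13 alone may not catch some older women with severely reduced eGFR (assumed cut below 30)

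*Combined protocol and SAP*

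**What the plan says.** Exclusion Criteria, item 13, of the combined protocol and SAP reads: "Subject has severe renal impairment or End Stage Renal disease (i.e., creatinine greater than 2.0 mg/dl". The 'i.e.' makes that creatinine value the working definition of the condition. A value of exactly 2.0 mg/dl passes. The document does not mention eGFR or creatinine clearance.

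Other parts of the plan that bear on this:

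- **Population.** Study Subjects describes "Male and female subjects presenting with planned stent placement for ureteral obstruction or post-ureteroscopy procedures for stone". Inclusion 1 sets a minimum age of 18 and no maximum.
- **Source of the creatinine.** Study Methods: "Subjects will undergo a blood draw prior to stent placement (complete blood count (CBC), comprehensive metabolic panel (CMP) and urine analysis". The tests are not repeated if routine preoperative work-up already supplied them.
- **Dose.** Study Methods gives 50 mg daily, which "will be administered in the treatment group for up to 4 weeks initiated on the day of stent placement". No reduced dose is described.
- **Other entry conditions.** Inclusion 3: "Otherwise healthy subjects who are able and willing to participate in the study". Inclusion 4: "None of the planned interventions are documented in the labeled contraindications, warnings and precautions of the study drug".
- **Follow-up.** In the schedule of assessments, the row "Laboratory screening tests (hematology & chemistry" is marked at baseline only. The row "Review Adverse Events" is marked at every later contact. Blood pressure and heart rate are taken at stent removal and early withdrawal.

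**The concern.** Item 13 shows that the authors wanted patients with severe renal impairment kept out. A flat creatinine value does this unevenly, because the same creatinine corresponds to lower kidney function in a woman than in a man, and in an older patient than in a younger one. A cap that is strict for men can be loose for older women.

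This matters because screening is the only scheduled check of renal function. After it, the active arm takes a fixed dose for up to 4 weeks, and none of the scheduled follow-up measures assesses the kidney. The issue is one of eligibility and safety wording. It does not affect the sample size, the endpoints or the analysis.

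**Working it through.** The 2.0 mg/dl value is a definition, so there is no derived figure to reproduce. The check asks what eGFR a patient can have and still pass item 13.

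**Inputs from the plan:** creatinine cap 2.0 mg/dl (item 13); both sexes (Study Subjects); age 18 or older (inclusion 1).

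**Assumptions, not in the plan:** severe means eGFR below 30; the three equations below; body weights of 60 to 90 kg.

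**CKD-EPI 2021** (creatinine above k): eGFR = 142 × (Cr/k)^−1.2 × 0.9938^age, × 1.012 in women, with k = 0.7 for women and 0.9 for men. Solving for the creatinine that gives 30 in a woman: Cr = 0.7 × (142 × 1.012 × 0.9938^age / 30)^(1/1.2).

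Example, woman aged 70: 0.9938^70 = 0.647; 142 × 1.012 × 0.647 = 92.98; 92.98/30 = 3.10; 3.10^(1/1.2) = 2.57; × 0.7 = 1.80 mg/dl. At the cap: 92.98 × (2.0/0.7)^−1.2 = 92.98 × 0.2837 = 26.4.

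**MDRD:** eGFR = 175 × Cr^−1.154 × age^−0.203, × 0.742 in women.

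**Cockcroft-Gault** (mL/min): (140 − age) × weight / (72 × Cr), × 0.85 in women. Example, woman aged 70, 60 kg, creatinine 2.0: 70 × 60 × 0.85 / 144 = 24.8.

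Results for women:

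| Age | Cr giving 30, CKD-EPI 2021 | Gap below 2.0 | Cr giving 30, MDRD | Gap below 2.0 | eGFR at 2.0, CKD-EPI 2021 | eGFR at 2.0, MDRD | Cockcroft-Gault at 2.0, 60 / 70 / 80 / 90 kg |
|---|---|---|---|---|---|---|---|
| 60 | 1.89 | 0.11 | 1.73 | 0.27 | 28.1 | 25.4 | 28.3 / 33.1 / 37.8 / 42.5 |
| 70 | 1.80 | 0.20 | 1.69 | 0.31 | 26.4 | 24.6 | 24.8 / 28.9 / 33.1 / 37.2 |
| 80 | 1.71 | 0.29 | 1.65 | 0.35 | 24.8 | 24.0 | 21.2 / 24.8 / 28.3 / 31.9 |

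By CKD-EPI 2021 the gap opens at about age 50 (limit 1.99, gap 0.01). The two eGFR equations agree in direction. Cockcroft-Gault agrees for lighter women but not for heavier ones: at creatinine 2.0 it stays above 30 for a woman of 60 at 70 kg, of 70 at 80 kg, and of 80 at 90 kg.

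**Men.** At creatinine 2.0, CKD-EPI 2021 gives 37.5, 35.2 and 33.1 at ages 60, 70 and 80, and first falls below 30 at 96. The MDRD limits are 2.24, 2.18 and 2.13, all above the cap. By Cockcroft-Gault some light older men are below 30 (age 80, 70 kg: 60 × 70 / 144 = 29.2).

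**Sensitivity to the cut (CKD-EPI 2021, women).** With a cut of 25 the limit is 1.996 at age 79, 1.99 at 80 and 1.94 at 85, so only women of about 79 or older very near the cap are affected. With a cut of 20 the limit is 2.39 at 80 and 2.21 at 95, so none are. These two results belong to this equation. MDRD, for example, is already below 25 for a woman of 70 at creatinine 2.0 (24.6).

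**The case against.** The strongest reply is that the gap exists only under an imported definition. The plan defines severe impairment as creatinine above 2.0 mg/dl, and by that definition item 13 catches everyone it names. This stands. A reader might infer that the exclusion misses patients it sets out to exclude, but the documents support that only if severe is assumed to mean below 30, and the result shrinks quickly at lower cuts.

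Second, passing item 13 is not the same as being eligible. A reader might infer that these women would be enrolled. Inclusion 3 requires general good health, inclusion 4 points to the labelled warnings, and history and eligibility are reviewed at baseline. An investigator could turn such a woman away on those grounds. This also stands, with a limit: neither inclusion gives a renal number, and inclusion 4 is worded about interventions, not about the patient's kidney function. A coordinator checking a creatinine of 1.9 against item 13 would record a pass.

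Third, the finding depends on the equation. It does, for women by Cockcroft-Gault, as the table shows.

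Fourth, the eGFR equations assume stable creatinine, and some patients are stented for obstruction. A value taken before placement may be temporarily high. This weakens the existing cap as much as an added eGFR limit, but the added limit could exclude some women whose function would recover once stented. That is a real cost.

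Finally, a single cap is simple and easy to verify. The fix below keeps it.

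**Conclusion.** The point holds in a limited form: item 13 alone may not catch some older women whose eGFR is in the severe range, if severe means below 30. By CKD-EPI 2021 the uncaught creatinine band is 0.11 to 0.29 mg/dl wide between ages 60 and 80. It is somewhat wider by MDRD and weight-dependent by Cockcroft-Gault. The conclusion rests on an assumed cut and assumed equations.

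It does not extend to men in general: by CKD-EPI 2021 and MDRD the cap is already stricter than 30 for them up to very old age. Nor do the documents show that anyone would be harmed or given too high a dose. They state no renal dose limit for the drug, treatment lasts at most 4 weeks, and half of the 100 patients receive placebo. The number affected cannot be estimated from the plan. No endpoint, power statement or analysis changes. This is a cheap improvement for the sponsor to consider, not a flaw that threatens the trial.

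**What to change.** Keep the 2.0 mg/dl cap in item 13 and add after it: *or eGFR below 30 mL/min/1.73 m2 (CKD-EPI 2021)*. The sponsor should confirm both the cut and the equation against the drug labelling to which inclusion 4 refers. Calculate the eGFR at screening from the pre-placement creatinine that the cap already uses, with the age and sex already collected as baseline variables.

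The cost is one clause and one calculator step, with no new test. Because the clause can only exclude, nobody becomes newly eligible. A few older women become ineligible (about 50 or older by CKD-EPI 2021), some of whom may have a raised creatinine from reversible obstruction. Study Subjects reports about 350 stenting procedures a year, or about 700 over the 24-month enrolment period (2 × 350), for 100 patients. The effect on recruitment should therefore be small, although its exact size is unknown.

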Data analysis will be concluded upon the completion of the study. Subjects' age, height, weight, and other continuous baseline variables will be summarized using descriptive statistics, while gender, race and other categorical variables will be provided using frequency tabulations. Medical history data will be summarized using frequency tabulations by system organ class and preferred term. Chi-square and t-tests will be used, as appropriate, to compare percent change and mean change from baseline in the ISSI, voiding diary, narcotic log, VAS score and PGI-S at the final study visit (14 days) or at any early termination visit. A split-plot ANOVA with repeated measures will be used for each measure (ISSI, VAS and PGI-S) to compare groups (Myrbetriq™ and placebo) over time and to determine if there is an interaction between groups. Significance will be assumed when $p < 0.05$. A preliminary power analysis based on previously published data, using an estimated SD for each study group of 4.17, a sample size of 50 in each study group (Myrbetriq™ and placebo) has an 80% power to detect an ISSI difference of 25% between the two groups with a significance level (alpha) of 0.05 (two-tailed)¹².

Pertinent to each Specific Aim are the following calculations:

- Primary Endpoints: Comparison of the change from baseline in ISSI and voiding diaries between Myrbetriq™ and placebo will be made using an independent t test for continuous scoring and a chi-squared test for ordinal scoring. Inferential analyses of changes from base line in micturition episodes per 24 hours and incontinence episodes per 24 hours will be performed using a stratified rank analysis to compare to baseline and as a covariance for each treatment.
- Exploratory Endpoints: Comparison of the change from baseline of total VAS between Myrbetriq™ and placebo will be made using an independent t test for continuous scoring and a chi-squared test for ordinal scoring. Comparison of the change from baseline in PGI-S between Myrbetriq™ and placebo will be made using an independent t test for

continuous scoring and a chi-squared test for ordinal scoring. Comparison of pain medicine intake between Myrbetriq™ and placebo groups will be made using an independent t test.

Safety Considerations

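### Percent change from baseline is tested alongside mean change, although it is undefined at a zero baseline, unstable at a small one, and has no pre-stent denominator for the narcotic log

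*Combined protocol and SAP*

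**What the plan says.** The general paragraph of Statistical Analyses states: "Chi-square and t-tests will be used, as appropriate, to compare percent change and mean change from baseline in the ISSI". The sentence goes on to the voiding diary, narcotic log, VAS and PGI-S, and sets the time point "at the final study visit (14 days) or at any early termination visit". Significance is taken at p < 0.05. Nothing says which scale governs if the two disagree, or what happens when a baseline is zero.

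The endpoint bullets in the same section do not mention percent change:

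- For the primary endpoints: "Comparison of the change from baseline in ISSI and voiding diaries between Myrbetriq™ and placebo will be made using an independent t test", with a chi-squared test for ordinal scoring.
- For micturition and incontinence episodes, the analysis "will be performed using a stratified rank analysis to compare to baseline and as a covariance for each treatment".
- VAS and PGI-S are compared on change from baseline, and pain-medicine intake directly between arms.

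A split-plot ANOVA is also planned for ISSI, VAS and PGI-S.

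Baselines differ by measure. The assessment schedule puts ISSI, VAS and PGI-S in the Baseline/Stent Placement column and has no diary or pain-log entry there. Study Methods takes the diary baseline two weeks after the stent comes out, provided that is done by day 28, and starts the narcotic log after surgery.

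Inclusion Criteria set no minimum symptom level; one criterion reads "Otherwise healthy subjects who are able and willing to participate in the study". Exclusion Criteria remove, among others, a subject where "Subject has significant stress incontinence or mixed stress/urgency incontinence where stress is the predominant factor as determined by the investigator".

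**The concern.** A ratio to baseline needs a denominator that exists, is above zero and is not tiny. The trial studies symptoms that the stent brings on, in subjects who need have none beforehand, so low baselines are to be expected for at least some measures. A subject at zero has no percent change. A subject at 1 or 2 points can show a rise of several hundred percent and dominate the arm mean.

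With no zero-baseline rule, the analyst must either leave such subjects out of this comparison or choose a convention (such as adding a constant) after seeing the data. The percent-change and mean-change tests can then disagree on the same data at the same threshold. This matters because Study Objective and Endpoints says that the pilot is to confirm an effect size and inform a larger study. An unstable percent figure is a poor quantity to carry forward.

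**Working it through.** **Inputs from Statistical Analyses.** "using an estimated SD for each study group of 4.17"; "a sample size of 50 in each study group"; two-sided alpha 0.05; 80% power for a 25% ISSI difference. The mean to which the 25% refers is not given.

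**1. The plan's own power figure.** Detectable difference = SD × (z₀.₉₇₅ + z₀.₈₀) × √(2/n) = 4.17 × (1.960 + 0.842) × √(2/50) = 2.34 points. With the noncentral t it is 0.566 × 4.17 = 2.36 points. This equals 25% only if the reference ISSI mean is 2.34 / 0.25 = 9.35 (9.44 with t). For reference means of 5, 8, 10 and 12, a 25% difference has 32%, 67%, 85% and 95% power. The stated 80% can be neither confirmed nor refuted. It serves here only to supply an effect of about 2.34–2.36 points on the absolute scale.

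**2. What the ratio does to one effect.** Assume a stent-related rise of 5 points on placebo and 5 − 2.36 = 2.64 on active treatment.

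| Baseline | Placebo | Active | Difference (percentage points) |
|---|---|---|---|
| 0 | undefined | undefined | – |
| 1 | 500% | 264% | 236 |
| 2 | 250% | 132% | 118 |
| 10 | 50% | 26.4% | 23.6 |

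The same effect in points counts ten times as much at baseline 1 as at baseline 10.

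**3. Loss of subjects alone.** Power = Φ(2.34 / (4.17 × √(2/n)) − 1.96), for assumed zero-baseline shares of 10, 20, 30, 40 and 50%. With n = 45, 40, 35, 30 and 25 per arm, power is 76%, 71%, 65%, 58% and 51%, against 80% at n = 50.

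**4. Simulated trials, first set of assumptions.** Gamma-Poisson baselines (shape 1.5) with mean m = 2, 4 or 8. The zero share is (1 + m/1.5)^(−1.5) = 28%, 14% or 6%. Follow-up is the subject mean + 5 − 2.36 if treated + normal noise (SD 3.5), floored at 0; 50 per arm, 3000 trials per setting. Power of the absolute-change t test: 85%, 81%, 73%. Power of the percent-change t test: 48%, 40%, 31%.

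**5. Second set of assumptions.** The zero share is set directly. Non-zero baselines are skewed with mean 4, 9.35 or 15; mean rise 6, SD of change 4.17, effect 2.34; 4000 trials per setting. Entries are power at the three means.

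| Zero share | Absolute change, all subjects | Percent change, baseline > 0 |
|---|---|---|
| 0% | 80 / 80 / 79% | 44 / 31 / 26% |
| 10% | 78 / 78 / 79% | 39 / 29 / 25% |
| 30% | 79 / 79 / 78% | 32 / 23 / 20% |
| 50% | 78 / 77 / 77% | 25 / 17 / 15% |

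The SD of percent change was about 110–275 percentage points. Power is lost even with no zeros, so small and uneven baselines matter as well as excluded subjects. A Mann-Whitney test on percent change did better than the t test (52–57% with no zeros, 29–31% with half zeros) but stayed below absolute change.

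**6. Measures where no simulation is needed.** The narcotic log has no pre-stent value for any subject, so there is nothing to divide by. For PGI-S the documents give no numeric coding, and the ratio depends on it: one step up from the lowest category is 100% if that category is coded 1 and undefined if it is coded 0.

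**The case against.** Most of the plan already avoids the problem. The endpoint bullets use change from baseline or ranks, PGI-S has a chi-squared option for ordinal scoring, and the ANOVA works on the scores. The study is an exploratory pilot that will rely primarily on descriptive statistics. All of this stands, and it limits the point to one comparison. A reader might infer that zero-baseline subjects are lost from the trial's main analysis, or that its power is reduced. The documents support neither: no text drops such subjects, and the other planned analyses can include them.

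The sentence could also be read as pairing chi-square with percentages of subjects who change and t tests with mean change, so that no one is divided by zero. That is possible, but it is not what percent change from baseline says, and no responder threshold is given to support it.

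A reader might also infer that the typical subject scores zero before the stent on everything. That goes too far. Stenting for obstruction is included and a single pre-procedure drug dose in the emergency room is foreseen, so acute pain at baseline is plausible and VAS is the weakest example. Chronic pain is excluded but acute pain is not, and urgency incontinence is not excluded. For ISSI, VAS and PGI-S a pre-stent baseline is a fair inference from the schedule, but the hour is not stated. For diary incontinence it would be wrong, because that baseline follows stent removal. A count of zero is still possible then.

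**Conclusion.** The point holds for the percent-change comparison only. As written, it has no defined value for a subject with a zero baseline, is dominated by subjects with baselines of 1 or 2, cannot be formed for the narcotic log, and has little meaning for PGI-S. It is also a second test at p < 0.05 with no stated standing relative to mean change.

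Its size cannot be obtained from the documents, which give no baseline means, zero shares or within-subject correlation. Both sets of assumptions agree in direction: 31–48% power against 73–85% in the first, and 15–44% against 77–80% in the second. These figures describe the percent-change t test. They say nothing against the endpoint-specific analyses. The correction is worth making because it is nearly free and removes a test that could contradict the mean-change result or be carried into the larger study.

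**What to change.** In the general paragraph of Statistical Analyses, delete the words 'percent change and', so that only absolute change (points, or episodes per 24 hours) is tested, in line with the endpoint bullets. In the same sentence:

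- Report PGI-S as category counts by arm.
- Remove the narcotic log from the change-from-baseline list and compare intake directly between arms, as the exploratory bullet already does.
- If a percent figure is wanted, give it descriptively as the ratio of group means, which needs no per-subject division.

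If the intended meaning was the percentage of subjects who change, say so and define the threshold.

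The cost is a short edit and no new data. The only loss is a tested percent figure that could not be computed for every subject. The edit does not settle the separate matter that the diary baseline is collected after stent removal.
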